#### **Early Withdrawal**

Subject discontinuation should be considered at the discretion of the principal investigator. The circumstances of any discontinuation have to be documented in detail. If possible, the evaluations planned for the end of study will be carried out at the time when the subject is withdrawn from the study.

Criteria for removal of subjects from the study will include:

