#### Protocol violation

Any subject found to have entered this study in violation of the protocol will be discontinued from the study at the discretion of the principal investigator. This will include any subject found to have been inappropriately enrolled (did not meet eligibility criteria). Subject non-compliance includes either not showing up for study visits, not taking investigational product as directed, or refusing to undergo study visit procedures. Subjects who are found to be less than 75% compliant with test article usage at any study visit will be withdrawn. Subjects who are found to be taking prohibited medications or supplements without the knowledge of the principal investigator will also be withdrawn. Any major protocol deviations (i.e., those that increase the risk to subjects and/or compromise the integrity of the study or its results) will result in subject discontinuation.

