#### Baseline - (Visit 1 / Week 0/ Day 0)

Subjects will receive the treatment regimen of LiGNO™ TMM.

Eligible subjects will return to the clinic in a fasted condition (last food intake at least 12 hours before the visit; subjects will be allowed to drink water) for baseline assessments:

- vitals signs, weight and height measurement
- Asthma Control Questionnaire
- review of concomitant therapies
- physical examination
- Review of spirometry measurements (FEV1 and FVC)
- Review of laboratory tests (basic hematology and chemistry)
- Review of urine pregnancy test for women of childbearing potential
- Review of baseline ECG

After all baseline assessments are reviewed, subjects will be dispensed the investigational product.

Subjects will receive LiGNO™ TMM. Subjects will be instructed in detail by site personnel about the dosing regimen. The first dose of study product is to be taken the day after the Baseline visit, treatment Day 1, consisting of :

• 2 capsules of 250 mg L. rhinocerus, once a day after breakfast and dinner daily for 4 weeks

Subjects will be given a diary card to record their symptoms every day. Subjects will be reminded to fast (12 hours) prior to their study visits. The next visit will be scheduled for Week 4/Day 30.

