#### Investigational Study Visit (Visit 2 / Week 4 / Day 30)

Subjects will return the clinic on Week 4 (Day 30). Any remaining investigational product or empty packaging will be returned and a new supply dispensed.

Study visit assessments will include:

- vitals signs, weight measurement
- review of concomitant therapies
- review of adverse events
- review of the diary card record
- symptoms examination
- compliance calculation
- Asthma Control Questionnaire
- Laboratory tests (basic hematology and chemistry)
- Exhaled nitric oxide (FENO) measurements
- ECG

Subjects will receive LiGNO™ TMM. Subjects will be instructed in detail by site personnel about the dosing regimen. Dosing will be escalated to

• 2 capsules of 250 mg L. rhinocerus, twice a day after breakfast and dinner daily for 8 weeks

Subjects will be reminded to fast (12 hours) prior to their study visits. The next visit will be scheduled for Day 60.

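### The first-month dose contradicts itself, and subjects under 75% compliance leave the study before the only scheduled post-baseline FEV1

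*Protocol*

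**What the plan says.** **Dose.** The Protocol's Baseline section (Visit 1) gives the only first-month dosing instruction: two capsules of 250 mg, "once a day after breakfast and dinner daily for 4 weeks". The same section adds: "Subjects will be instructed in detail by site personnel about the dosing regimen". At Visit 2 (Day 30) the Protocol states "Dosing will be escalated to" two capsules of 250 mg, "twice a day after breakfast and dinner daily for 8 weeks". Compliance is calculated at Visits 2, 3 and 4.

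**Withdrawal.** Under Protocol violation: "Subjects who are found to be less than 75% compliant with test article usage at any study visit will be withdrawn". That section is one of the grounds introduced under Early Withdrawal by "Criteria for removal of subjects from the study will include", so it removes the subject from the study and not only from the product. Early Withdrawal also says: "Subject discontinuation should be considered at the discretion of the principal investigator". For those who leave it provides: "If possible, the evaluations planned for the end of study will be carried out at the time when the subject is withdrawn".

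**FEV1 schedule.** The visit lists place spirometry at screening (with the results reviewed at baseline) and at Day 90. The Day 30 and Day 60 lists contain FeNO and the Asthma Control Questionnaire but no spirometry. Change in trough FEV1 after 90 days is one of the two primary endpoints.

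**The concern.** These are two independent problems.

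First, the dosing line cannot be followed as written. A site that takes its cue from the meal timing would give two capsules at each of two meals from Day 1. That is already the escalated dose, so the lower-dose month would disappear and the Day 30 FeNO, questionnaire, laboratory and ECG results would reflect twice the intended daily dose.

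Second, the compliance rule decides who contributes a Day 90 FEV1. A subject removed at Visit 2 or 3 has no scheduled FEV1 after baseline. If low adherers improve less than the others, the mean change among those left is too favourable, and a single-arm trial has no control group to reveal it. The other primary endpoint, ACQ-7, is less exposed because it is also collected at Days 30 and 60.

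**Working it through.** The Protocol states no figure for either point that could be reproduced, so the check is a reading of the text plus arithmetic.

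**Dose under each reading of the first-month line**

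| Reading | mg/day | Capsules in 28 days (30 days) | 75% cut-off |
|---|---|---|---|
| 2 capsules at one meal | 2 × 250 = 500 | 56 (60) | 42 (45) |
| 1 capsule at each of two meals | 2 × 250 = 500 | 56 (60) | 42 (45) |
| 2 capsules at each of two meals | 4 × 250 = 1000 | 112 (120) | 84 (90) |

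The Day 30 regimen is 2 × 2 × 250 = 1000 mg/day and is described as an escalation, so the first-month dose must be lower. Only 500 mg/day fits. The text does not settle whether it is taken at breakfast, at dinner or split.

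Total exposure over 4 + 8 weeks:
- intended: 28 × 0.5 g + 56 × 1.0 g = 70 g
- 1000 mg/day throughout: 84 × 1.0 g = 84 g
- ratio: 84/70 = 1.20, the extra 14 g all falling in month 1

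No reading exceeds 1000 mg/day.

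**How easily the withdrawal rule is met at Visit 2 (2 capsules a day)**

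- 7 of 28 days missed: 21/28 = 75.0%, not below the limit.
- 8 of 28 days missed: 20/28 = 71.4%, below the limit, so the subject is withdrawn.
- Removal at Day 30 comes 90 − 30 = 60 days before the scheduled FEV1.

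A subject found below 75% only at Visit 4 is already at the visit where spirometry is done, so the loss concerns Visits 2 and 3.

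**Effect on the mean FEV1 change**

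Let p be the share removed and d the mean change in retained subjects minus the mean change in removed subjects. The all-subject mean is (1 − p) × retained + p × removed, so

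retained mean − all-subject mean = p × d.

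Assumptions, not in the documents: 1 to 3 subjects removed, d = 100 to 200 mL, and no Day 90 value for those removed. The Protocol gives 17 subjects under Study Design and Sample Size and 10 under Study Population, so both are shown. The benchmark is the 200 mL part of the stated FEV1 MCID.

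| | 17 subjects | 10 subjects |
|---|---|---|
| Low end | 1/17 × 100 = 5.9 mL (2.9% of 200 mL) | 1/10 × 100 = 10 mL (5%) |
| High end | 3/17 × 200 = 35.3 mL (17.6%) | 3/10 × 200 = 60 mL (30%) |

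If d = 0 there is no bias. The standard error then rises by these factors for 1 and 3 removed:
- 17 subjects: √(17/16) = 1.031 to √(17/14) = 1.102
- 10 subjects: √(10/9) = 1.054 to √(10/7) = 1.195

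**The case against.** **On the dose.** The word escalated lets a careful reader recover 500 mg/day, staff instruct each subject in detail, and every listed efficacy endpoint is a 90-day change, by which time all readings give 1000 mg/day. The +20% exposure arises only under a reading that does not fit the Day 30 text. All of this stands and limits the consequence. It does not make the line usable: it is the only first-month instruction, and the meal timing cannot be inferred. If a site instructed 500 mg/day but counted against 112 capsules, a fully adherent subject would score 56/112 = 50% and be withdrawn. That requires the same staff to instruct one dose and count another, so it is possible but not expected.

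**On withdrawal.**
- *An exit evaluation is planned and would include spirometry, and its use in the analysis can be left to a SAP.* This stands in part: FEV1 is not necessarily lost, and the figures above do not apply as they are if exit values are used. But the evaluation is conditional, and at Visit 2 or 3 it yields a Day 30 or Day 60 value. No SAP can recover a Day 90 measurement that the Protocol stops collecting.
- *The number removed and the difference in response are assumed.* True; the bias figures are illustrative.
- *The 200 mL benchmark is loose, because the Protocol ties that MCID to a 2-hour post-dose FEV1 while the endpoint is trough.* True; the percentages only give a sense of scale.
- *Study Design and Sample Size says assessments for the primary and secondary outcomes take place at Days 0, 30, 60 and 90.* That is a general statement. The itemised lists for Days 30 and 60 contain no spirometry, and sites work from those lists.
- *A general discretion clause can sit alongside a specific mandatory rule.* It can, but two investigators could still treat the same subject differently, so the wording should be aligned.

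**Conclusion.** Both parts hold, each on its own, and both should be fixed; neither is fatal.

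The first-month line contradicts itself. The intended dose is 500 mg/day, inferred from the escalation at Day 30, and the consequence of misreading it is confined to month 1 exposure and the Day 30 data.

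The withdrawal rule does remove low adherers before the only scheduled post-baseline FEV1, with a conditional early value as the sole substitute. That follows from the text. The size of any bias does not: 5.9 to 35.3 mL (17 subjects) or 10 to 60 mL (10 subjects) depends on the assumed removals, the assumed difference in response and no use of exit values. If adherence and response are unrelated, the cost is a standard error 3% to 10% larger (17 subjects) or 5% to 20% larger (10 subjects).

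**What to change.** **Baseline section.** State two capsules (500 mg) per day with one meal timing, from Day 1 to Visit 2, subject to the sponsor's confirmation. Calculate Visit 2 compliance against two capsules a day (56 over 28 days, 60 over 30).

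**Protocol violation section.** Replace mandatory withdrawal below 75% with: such subjects may stop product, but remain in follow-up for the scheduled Day 90 assessments, including spirometry, and are included in the analysis. Align Early Withdrawal with this, separating stopping product from leaving the study.

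**Cost.** One corrected dosing line with matching subject instructions, one changed sentence and its alignment. The Day 60 and Day 90 visits are already scheduled but must actually be held for these subjects. The estimated effect may come out smaller, by up to the amounts above under the stated assumptions.

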#### Investigational Study Visit (Visit 2 / Week 4 / Day 30)

Subjects will return the clinic on Week 4 (Day 30). Any remaining investigational product or empty packaging will be returned and a new supply dispensed.

Study visit assessments will include:

- vitals signs, weight measurement
- review of concomitant therapies
- review of adverse events
- review of the diary card record
- symptoms examination
- compliance calculation
- Asthma Control Questionnaire
- Laboratory tests (basic hematology and chemistry)
- Exhaled nitric oxide (FENO) measurements
- ECG

Subjects will receive LiGNO™ TMM. Subjects will be instructed in detail by site personnel about the dosing regimen. Dosing will be escalated to

• 2 capsules of 250 mg L. rhinocerus, twice a day after breakfast and dinner daily for 8 weeks

Subjects will be reminded to fast (12 hours) prior to their study visits. The next visit will be scheduled for Day 60.

#### Investigational Study Visit (Visit 3 / Week 8 / Day 60)

Subjects will return the clinic on Week 8 (Day 60). Any remaining investigational product or empty packaging will be returned and a new supply dispensed.

Study visit assessments will include:

- vitals signs, weight measurement
- review of concomitant therapies
- review of adverse events
- review of the diary card record
- symptoms examination
- compliance calculation
- Asthma Control Questionnaire
- Laboratory tests (basic hematology and chemistry)
- Exhaled nitric oxide (FENO) measurements
- ECG

Subjects will be reminded to fast (12 hours) prior to their study visits. The next visit will be scheduled for Week 12/Day 90.

# End of Treatment Visit (Visit 4 / Week 12/ Day 90) - CIC

Subjects will return the clinic on Day 90. Any remaining investigational product or empty packaging will be returned.

Study visit assessments will include:

- vitals signs, weight measurement
- review of concomitant therapies
- review of adverse events
- review of the diary card record
- symptoms examination
- compliance calculation
- Asthma Control Questionnaire
- Laboratory tests (basic hematology and chemistry)
- Exhaled nitric oxide (FENO) measurements, followed by
- Spirometry measurement (FEV1 and FVC)
- ECG

This visit will conclude the study.

#### **Grant and Funding**

This research is supported by the University Malaya Faculty Research Grant (UMFRG) 2020.

